9.5.3 Appropriateness of Measurements

All clinical assessments are standard measurements used to meet the requirements for conducting a CVOT.

The safety assessments to be performed in this study, including hematology analyses, blood chemistry tests, urinalysis, vital signs and assessment of AEs, are standard evaluations to ensure subject safety. Serial echocardiogram assessments on a subset of subjects at selected sites are included in the study per requirement by the FDA.

9.5.4 Reporting of SAEs, Hypoglycemia, Pregnancy, and Other Events of Interest

9.5.4.1 Reporting of SAEs

All SERIOUS ADVERSE EVENTS, regardless of their relationship to study treatment, must be reported as soon as possible but no later than 24 hours from the time the investigator becomes aware of the event.

Serious adverse events, regardless of causality assessment, must be collected through the end of study. For those subjects taking study drug at the time of study completion (“Sponsor Notification of Study Completion”), SAEs should be collected for 30 days after the last dose. (revised per Amendment 01) All SAEs must be followed to resolution or, if resolution is unlikely, to stabilization. Any SAE judged by the investigator to be related to the study treatment should be reported to the sponsor regardless of the length of time that has passed since study completion.

The detailed contact information for reporting of SAEs is provided in the Investigator Study File.

For urgent safety issues, please ensure all appropriate medical care is administered to the subject and contact the appropriate study team member listed in the Investigator Study File.

It is very important that the SAE report be as complete as possible at the time of the initial report. This includes the investigator’s assessment of causality.

Any follow-up information received on SAEs should be forwarded within 24 hours of its receipt. If the follow-up information changes the investigator’s assessment of causality, this should also be noted on the follow-up SAE report.

Preliminary SAE reports should be followed as soon as possible by detailed descriptions including copies of hospital case reports, autopsy reports, and other documents requested by the sponsor.

The investigator must notify his/her IRB/IEC of the occurrence of the SAE, in writing, if required by their institution. A copy of this communication must be forwarded to the sponsor or designated CRO to be filed in the sponsor’s Trial Master File.

9.5.4.2 Reporting of Hypoglycemia

Patient-reported episodes of hypoglycemia or decreased blood sugar should be captured on the eCRF according to the following guidelines:

- Mild hypoglycemia is defined as capillary glucose ≥ 55 to < 65 mg/dL (≥ 3.0 - < 3.3 mmol/L) that the subject is able to treat himself/herself; or, if glucose is not measured, symptoms of hypoglycemia that resolve with administration of oral carbohydrates.
- Moderate hypoglycemia is defined as capillary glucose < 55 mg/dL (< 3.0 mmol/L) that the subject is able to treat himself/herself.
- Severe hypoglycemia is defined as a symptomatic capillary glucose < 40 mg/dL (< 2.2 mmol/L) OR a capillary glucose ≤ 65 mg/dL AND needed help from another person OR required intravenous glucose
- Catastrophic hypoglycemia is defined as severe hypoglycemia that resulted in life-threatening injury to the subject or another person, hospitalization, and/or death. This should be reported as a SAE.

Additionally, **adverse events** of hypoglycemia should be further specified in the eCRF adverse event term as “symptomatic” or “asymptomatic”.

See [Section 9.4.7.2](#) for directions on the recommendations for possible adjustment to antihyperglycemic medication doses in response to reported episodes of hypoglycemia.

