- Medications for the treatment of hypertension, dyslipidemia, or diabetes may be started, discontinued, or adjusted during the study according to local standards of care if, in the judgment of the investigator or the subject's physician, such a change is medically indicated.
- For diabetic subjects treated with sulfonylureas, insulin, or other antidiabetic agents with hypoglycemic risk, the risk of hypoglycemic events may be higher if the subjects experience rapid and significant weight loss (more than 10% weight reduction than at the previous visit). It is recommended that the physician advise the subject to monitor their blood glucose more frequently and adjust their antidiabetic medications and diet accordingly.
- The antihyperglycemic medication dose would be considered for reduction in the event of 1 documented and otherwise unexplained hypoglycemic event (blood glucose concentration <65 mg/dL) or 2 undocumented and otherwise unexplained suspected hypoglycemic events between any 2 scheduled visits. (revised per Amendment 01) For subjects on more than 1 antihyperglycemic medication, it is recommended to reduce insulin first (if applicable), then the oral and/or other injectable antidiabetic agents. If the previous criteria are met again following dose reduction, further dose reductions or

cessation of 1 or more anti-hyperglycemic agents, are suggested. See [Section 9.5.4.2](#) for the definition and reporting of hypoglycemic events.

- To minimize the risk of cardiac valve toxicity:
 - Subjects must not initiate use of agents that have documented correlation with increased incidence of valvulopathy and/or PH (eg, pergolide, ergotamine, methysergide, or cabergoline) during the study. (revised per Amendment 01) If any of the above agents are clinically warranted, and subjects initiate any of these agents, lorcaserin HCl should be discontinued but can be restarted on lorcaserin HCl after being off the medications above for 1 month. Otherwise, the study medication should not be restarted, but the subject should continue all study visits.
- Use of serotonergic drugs:

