Abnormal laboratory values should not be listed as separate AEs if they are considered to be part of the clinical syndrome that is being reported as an AE. Any laboratory abnormality considered to constitute an AE should be reported on the Adverse Event CRF.

It is the responsibility of the investigator to review all laboratory findings in all subjects and determine if they constitute an AE. Medical and scientific judgment should be exercised in deciding whether an isolated laboratory abnormality should be classified as an AE.

(revised per Amendment 01)

All AEs must be followed for at least 30 days after Sponsor Notification of Study Completion, or until resolution, whichever comes first. (revised per Amendment 01)

Every effort must be made by the investigator to categorize each AE according to its severity and its relationship to the study treatment.

ASSESSING SEVERITY OF AEs

AEs will be graded on a 3-point scale (mild, moderate, severe) and reported in the detail indicated on the CRF. The definitions are as follows:

Mild	Discomfort noticed, but no disruption of normal daily activity
Moderate	Discomfort sufficient to reduce or affect normal daily activity
Severe	Incapacitating, with inability to work or to perform normal daily activity

The criteria for assessing severity are different than those used for seriousness (see SAEs and Other Events of Interest, [Section 9.5.1.5](#) for the definition of an SAE).

ASSESSING RELATIONSHIP TO STUDY TREATMENT

Items to be considered when assessing the relationship of an AE to the study treatment are:

- Temporal relationship of the onset of the event to the initiation of the study treatment
- The course of the event, especially the effect of discontinuation of study treatment or reintroduction of study treatment, as applicable
- Whether the event is known to be associated with the study treatment or with other similar treatments
- The presence of risk factors in the study subject known to increase the occurrence of the event
- The presence of nonstudy, treatment-related factors that are known to be associated with the occurrence of the event

CLASSIFICATION OF CAUSALITY

Causality will be based on the response to the following question:

Was there a reasonable possibility that the drug caused the adverse event? Yes/No

Where Yes = related and No = Not related

SAES AND EVENTS ASSOCIATED WITH SPECIAL SITUATIONS

(revised per Amendment 01)

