Glucose, serum-high (hyperglycemia)	Fasting glucose value: > ULN – 160 mg/dL > ULN – 8.9 mmol/L	Fasting glucose value: > 160 – 250 mg/dL > 8.9 – 13.9 mmol/L	> 250 – 500 mg/dL; > 13.9 – 27.8 mmol/L; hospitalization indicated	> 500 mg/dL; > 27.8 mmol/L; life-threatening consequences
Glucose, serum-low (hypoglycemia)	< LLN – 55 mg/dL < LLN – 3.0 mmol/L	< 55 – 40 mg/dL < 3.0 – 2.2 mmol/L	< 40 – 30 mg/dL < 2.2 – 1.7 mmol/L	< 30 mg/dL < 1.7 mmol/L life-threatening consequences; seizures
Phosphate, serum-low (hypophosphatemia)	< LLN – 2.5 mg/dL < LLN – 0.8 mmol/L	< 2.5 – 2.0 mg/dL < 0.8 – 0.6 mmol/L	< 2.0 – 1.0 mg/dL < 0.6 – 0.3 mmol/L	< 1.0 mg/dL < 0.3 mmol/L life-threatening consequences
Potassium, serum-high (hyperkalemia)	> ULN – 5.5 mmol/L	> 5.5 – 6.0 mmol/L	> 6.0 – 7.0 mmol/L hospitalization indicated	> 7.0 mmol/L life-threatening consequences
Potassium, serum-low (hypokalemia)	< LLN – 3.0 mmol/L	< LLN – 3.0 mmol/L; symptomatic; intervention indicated	< 3.0 – 2.5 mmol/L hospitalization indicated	< 2.5 mmol/L life-threatening consequences
Sodium, serum-high (hyponatremia)	> ULN – 150 mmol/L	> 150 – 155 mmol/L	> 155 – 160 mmol/L hospitalization indicated	> 160 mmol/L life-threatening consequences
Sodium, serum-low (hyponatremia)	< LLN – 130 mmol/L	N/A	< 130 – 120 mmol/L	< 120 mmol/L

	Grade 1	Grade 2	Grade 3	Grade 4
				life-threatening consequences
Triglyceride, serum-high (hypertriglyceridemia)	150 – 300 mg/dL 1.71 – 3.42 mmol/L	> 300 – 500 mg/dL > 3.42 – 5.7 mmol/L	> 500 – 1000 mg/dL >5.7 – 11.4 mmol/L	> 1000 mg/dL > 11.4 mmol/L life-threatening consequences
Uric acid, serum-high (hyperuricemia)	> ULN – 10 mg/dL ≤ 0.59 mmol/L without physiologic consequences	N/A	> ULN – 10 mg/dL ≤ 0.59 mmol/L with physiologic consequences	> 10 mg/dL > 0.59 mmol/L life-threatening consequences

ALT = alanine aminotransferase (serum glutamic pyruvic transaminase), AST = aspartate aminotransferase (serum glutamic oxaloacetic transaminase), GGT = γ -glutamyl transpeptidase, LLN = lower limit of normal, N/A = not applicable, ULN = upper limit of normal, WBC = white blood cell.

Based on Common Terminology Criteria for Adverse events (CTCAE) Version 4.0. Published: May 28, 2009 (v4.03: June 14, 2010).

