#### 5.3.4 Examination of Subgroups

The primary endpoints will be analyzed for each of the demographic and baseline characteristics subgroups listed in Tables 2, and Baseline Cardiovascular Risk Level and Risk Factors, listed in Table 3. For categorical parameters, categories with sparse number of subjects will be collapse. The final set of categories will be determined prior to database lock.

Table 2 Subgroups of Demographic and Baseline Characteristics

Characteristic	Categories	
Age	≤65, ≥65 to < 75, ≥75 years	
Gender	Female, Male	
Race	White Black or African American Other Asian American Indian or Alaska Native Native Hawaiian or Other Pacific Islander Other	
BMI	$< 30 \text{ kg/m}^2$ $\ge 30 \text{ to} < 35 \text{ kg/m}^2$ $\ge 35 \text{ to} < 40 \text{ kg/m}^2$ $\ge 40 \text{ kg/m}^2$	
Waist circumference	Women <35 Inches (88cm) ≥35 Inches (88cm) Men <40 Inches (102cm) ≥40 Inches (102cm)	
Weight	$\leq 1^{st}$ Quartile >1 st Quartile to $\leq 2^{nd}$ Quartile >2 nd Quartile to $\leq 3^{rd}$ Quartile > 3 rd Quartile	
Duration of Type 2 Diabetes (years)	< 5 years     ≥ 5 to < 10 years     ≥ 10 to < 20 years     ≥ 20 years	
HbA1C	Non-diabetics (see Section 8)  Normal ( $< 5.7\%$ )  Pre-diabetes ( $\ge 5.7\%$ to $< 6.5\%$ )  Diabetics (see Section 8) $< 6.5\%$ $\ge 6.5\%$ to $< 7\%$ $\ge 7$ to $< 8\%$ $\ge 8$ to $< 9\%$ $\ge 9\%$	

Table 2 Subgroups of Demographic and Baseline Characteristics

Characteristic	Categories
FPG	<pre>< 100 mg/dL ≥ 100 to < 126 mg/dL ≥ 126 to < 150 mg/dL [≥ 7.0 mmol/L to < 8.3 mmol/L] ≥ 150 to < 220 mg/dL [≥ 8.3 mmol/L to < 12.2 mmol/L] ≥ 220 to < 300 mg/dL [≥ 12.2 mmol/L to < 16.7 mmol/L] ≥ 300 mg/dL [≥ 16.7 mmol/L]</pre>
Blood Pressure	Systolic BP (mmHg) <140 ≥140 Diastolic BP (mmHg) <90 ≥90
Renal Function (eGFR)	> 60 mL/min ≥ 30 to ≤ 60 mL/min < 30 mL/min
Albumin/creatinine ratio	<pre>< 30 mg/g [< 3.4mg/mmol]</pre>
Region and Country	North America (US/Canada) Rest of World (ROW) Europe Central and South America Australia/NZ
Baseline Diabetic Medication use	No medications/any insulin/oral meds without insulin GLP1 agonist/no GLP1 agonist SGLT2 inhibitor/no SGLT2 inhibitor SFU/no SF Metformin/no metformin SFU and Metformin/others Insulin/no insulin Insulin and SFU/others

Table 2 Subgroups of Demographic and Dasenic Characteristic	Table 2	Subgroups of Demographic and Baseline Characteristics
---	---------	---

Characteristic	Categories
	ASA

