#### **5.6.2** Adverse Events

The AE verbatim descriptions (investigator terms from the CRF) will be classified into standardized medical terminology using the Medical Dictionary for Regulatory Activities (MedDRA - Version 16.0 or higher). AEs will be coded to the MedDRA lower level term (LLT) closest to the verbatim term. The linked MedDRA preferred term (PT) and primary system organ class (SOC) are also captured in the database.

All AEs observed during the study will be reported on the CRF. All AEs, regardless of relationship to study drug or procedure, should be collected beginning from the time the subject signs the study ICF through the end of the study and for a minimum of 30 days after the last dose. Serious AEs will be collected through the end of study, and for a minimum of 30 days after the last dose.

A treatment-emergent AE (TEAE) is defined as an AE that emerges during treatment, having been absent at pretreatment (Baseline) or

- Reemerges during treatment, having been present at pretreatment (Baseline) but stopped before treatment, or
- Worsens in severity during treatment relative to the pretreatment state, when the AE is continuous.

Only those AEs that were treatment emergent (including CEC adjudicated events) will be included in summary tables. All AEs, treatment emergent or otherwise, will be presented in subject data listings.

TEAEs will be summarized by treatment group on the Safety Analysis Set. The incidence of TEAEs will be reported as the number (percentage) of subjects with TEAEs by SOC and PT (these summaries will be done with and without CEC adjudicated events). A subject will be counted only once within a SOC and PT, even if the subject experienced more than one TEAE within a specific SOC and PT. The number (percentage) of subjects with TEAEs will also be summarized by maximum severity (mild, moderate, or severe). The number (percentage) of subjects with TEAEs will also be summarized by relationship to study drug (Yes = related, and No = Not related).

AEs will be summarized by the following subgroups: age (< 65 years,  $\geq$  65 years to <75 years,  $\geq$ 75 years), sex (male, female), race (white, black, other), presence of established CV disease or CV risk factors without established CV disease, pre-diabetes at Baseline, and T2DM at Baseline (with and without).

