    - o random plasma glucose > or = 200 with associated symptoms of hyperglycemia prior to or at Baseline
- Subject who are Pre-diabetic at Baseline: Subject must meet all the following conditions;
  - o On the Diabetes History Form "Clinical diagnosis of diabetes?" = "No" and
  - o Not initiated any diabetes treatment prior to or at Baseline and
  - At least one of the following:
    - o HbA1c 5.7% to <6.5% or
    - FPG 100 to 125 mg/dL (5.55 to 6.94 mmol/L) between Screen and Baseline and
  - None of the following where available
    - o HbA1c  $\geq$  6.5% in all central or local labs assessments prior to or at Baseline and
    - o FPG ≥ 126 mg/dL (7.0 mmol/L) in all central or local labs assessments prior to or at Baseline and
    - o random plasma glucose > or = 200 with associated symptom of hyperglycemia prior to or at Baseline and
    - o 2-hour plasma glucose ≥ 200 mg/dL(11.1mmol/L) by an OGTT test prior to or at Baseline and
- Subject who are Normoglycemic at Baseline: Subject must meet the following conditions:
  - o On the Diabetes History Form "Clinical diagnosis of diabetes?" = "No" AND
  - o Not initiated any diabetes treatment prior to or at Baseline AND
  - o None of the following where available:
    - o HbA1c  $\geq$  5.7% in all central or local labs assessments prior to or at Baseline

- o FPG ≥ 100 mg/dL (5.55 mmol/L) in all central or local labs assessments prior to or at Baseline
- 2-hour plasma glucose ≥ 200 mg/dL(11.1mmol/L) by an OGTT test prior to or at Baseline
- Random glucose > or = 200 with associated symptoms of hyperglycemia prior to or at Baseline
- Subject is not otherwise defined as 'pre-diabetic' at baseline
- Subjects who are T2DM at Baseline: Subject must meet at least one of the following conditions.
  - o On the Diabetes History Form "Clinical diagnosis of diabetes?" = "Yes" and Type of Diabetes = 2 on Diabetic History CRF or
  - o HbA1c  $\geq$  6.5% prior to or at Baseline in either central or local labs or
  - o FPG ≥ 126 mg/dL (7.0 mmol/L) prior to or at Baseline in either central or local labs or
  - o 2-hour plasma glucose  $\geq 200 \text{ mg/dL}(11.1 \text{mmol/L})$  by an OGTT test or
  - Random plasma glucose > or = 200 with associated symptoms of hyperglycemia prior to or at Baseline
  - o Any diabetes treatment prior to or at Baseline
- Subjects who are T1DM at Baseline: Subject must meet the following conditions.

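### Protocol 9.5.4.2 gives 65 mg/dL as 3.3 mmol/L in the Mild hypoglycemia limit; it is 3.6 mmol/L, so in mmol/L self-treated readings of 60–64 mg/dL fit no category

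*Protocol*

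**What the plan says.** Protocol 9.5.4.2 tells sites how to classify patient-reported hypoglycemia on the eCRF. For a measured capillary glucose:

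- **Mild:** at least 55 and below 65 mg/dL, self-treated. The mmol/L range in parentheses runs from 3.0 to below "3.3 mmol/L) that the subject is able to treat himself/herself". A symptoms-only route exists, but only when glucose was not measured.
- **Moderate:** below 55 mg/dL (3.0 mmol/L), self-treated.
- **Severe:** symptomatic and below 40 mg/dL (2.2 mmol/L), or at most "65 mg/dL AND needed help from another person", or intravenous glucose required. The 65 mg/dL limit here has no mmol/L figure.
- **Catastrophic:** a severe episode with life-threatening injury, hospitalization or death.

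Protocol 9.4.7.2 uses the same 65 mg/dL limit, in mg/dL only, as a trigger for considering a reduction of antihyperglycemic medication: a "hypoglycemic event (blood glucose concentration <65 mg/dL". It sends the reader to 9.5.4.2 for the definition of hypoglycemic events.

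**The concern.** The Mild definition gives its upper limit in two units, and the two figures should describe the same glucose. If they do not, a site reading mg/dL and a site reading mmol/L will classify the same episode differently. Because the mmol/L figure is the lower of the two, it opens a gap at the top of the Mild band that no other category fills. The instruction governs eCRF capture in a trial where about half the subjects have type 2 diabetes, so at stake is consistent grading of measured, self-treated mild episodes across sites.

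**Working it through.** **Inputs.** The limits are those of Protocol 9.5.4.2. The formula is mmol/L = mg/dL ÷ 18.016. The documents imply nearly the same factor themselves (Protocol 9.3.1): 126 ÷ 7.0 = 18.0 and 200 ÷ 11.1 = 18.02.

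**Step 1: try to reproduce the plan's figure.** 65 ÷ 18.016 = 3.608 mmol/L, against 3.3 printed. Factors of 18.0 and 18.0182 give 3.611 and 3.607. The printed pair needs a factor of 65 ÷ 3.3 = 19.7. Converting back, 3.3 × 18.016 = 59.45 mg/dL. The figure is not reproduced; it is 0.308 mmol/L too low.

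**Step 2: is this only loose rounding?** The other glucose pairs come from Protocol 9.5.4.2 and Appendix 3 (for example "< 55 – 40 mg/dL < 3.0 – 2.2 mmol/L"), SAP 5.3.4 Table 2 (for example "126 to < 150 mg/dL [≥ 7.0 mmol/L to < 8.3 mmol/L") and SAP Section 8 (for example "FPG 100 to 125 mg/dL (5.55 to 6.94 mmol/L) between Screen and Baseline").

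| mg/dL | Printed mmol/L | Converted | Converted − printed |
|---|---|---|---|
| 30 | 1.7 | 1.665 | −0.035 |
| 40 | 2.2 | 2.220 | +0.020 |
| 55 | 3.0 | 3.053 | +0.053 |
| **65** | **3.3** | **3.608** | **+0.308** |
| 100 | 5.55 | 5.551 | +0.001 |
| 125 | 6.94 | 6.938 | −0.002 |
| 126 | 7.0 | 6.994 | −0.006 |
| 150 | 8.3 | 8.326 | +0.026 |
| 160 | 8.9 | 8.881 | −0.019 |
| 200 | 11.1 | 11.101 | +0.001 |
| 220 | 12.2 | 12.211 | +0.011 |
| 250 | 13.9 | 13.877 | −0.023 |
| 300 | 16.7 | 16.652 | −0.048 |
| 500 | 27.8 | 27.753 | −0.047 |

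The largest gap among the other 13 is 0.053, and 0.308 ÷ 0.053 = 5.8. Only the 65 mg/dL pair fails.

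**Step 3: which of the two figures is wrong?** 65 mg/dL recurs in the Severe definition and in Protocol 9.4.7.2. Nothing else in the documents supports 3.3 as a glucose limit, and nothing corrects it. The mmol/L figure is the error.

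**Step 4: classify each whole mg/dL value in the Mild band by the printed mmol/L limits.** The episode is measured and self-treated, with no help and no intravenous glucose.

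| mg/dL | Unrounded mmol/L | Category | One-decimal reading | Category |
|---|---|---|---|---|
| 55 | 3.053 | Mild | 3.1 | Mild |
| 56 | 3.108 | Mild | 3.1 | Mild |
| 57 | 3.164 | Mild | 3.2 | Mild |
| 58 | 3.219 | Mild | 3.2 | Mild |
| 59 | 3.275 | Mild | 3.3 | none |
| 60 | 3.330 | none | 3.3 | none |
| 61 | 3.386 | none | 3.4 | none |
| 62 | 3.441 | none | 3.4 | none |
| 63 | 3.497 | none | 3.5 | none |
| 64 | 3.552 | none | 3.6 | none |

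The values marked none are not below 3.3 (Mild), not below 3.0 (Moderate), and not below 2.2 (Severe). The symptoms-only route is closed because glucose was measured. The count is 5 of 10 unrounded and 6 of 10 on a one-decimal meter. These are counts of glucose values, not shares of episodes.

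**Step 5: repeat with an upper limit of 3.6.** Unrounded, none of the 10 values is left out. On a one-decimal meter only 64 mg/dL is left out, because it shows as 3.6 (and 3.6 × 18.016 = 64.86 mg/dL).

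**The case against.** The strongest reply is that mg/dL governs. Each glucose category is stated first in mg/dL, with mmol/L in parentheses, and the Severe limit of 65 mg/dL has no mmol/L figure at all, so a site using mmol/L must convert in any case. A reading of 3.4 mmol/L is 61 mg/dL and meets the mg/dL definition of Mild. On that view the limits conflict, but no episode lacks a category. This is a fair reading, but the protocol does not say which unit prevails, and a site that reports in mmol/L has every reason to use the mmol/L limits printed for it.

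The second reply is that nothing follows from the error, and most of this stands:

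- The SAP tabulates adverse events on a general scale: "The number (percentage) of subjects with TEAEs will also be summarized by maximum severity (mild, moderate, or severe". Protocol 9.5.1.5 defines that scale by effect on daily activity, with its mildest grade as "Discomfort noticed, but no disruption of normal daily activity", and not by glucose.
- The Appendix 3 grading of low serum glucose uses other limits, and these convert correctly.
- The dose-reduction trigger in Protocol 9.4.7.2 is in mg/dL only. Its cross-reference to 9.5.4.2 could mislead a mmol/L reader, but the documents do not show that it did.
- Serious-event reporting of catastrophic episodes does not depend on the Mild upper limit.
- Section 9.5.4.2 asks for reported episodes to be captured, so lost episodes are not shown.
- The CRF Completion Guidelines named in Protocol 9.6.1 are not among the documents and may state units or limits.

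A last reply is that one-decimal meters create mismatches anyway. At the lower limit, 54 mg/dL is 2.997 mmol/L and shows as 3.0, which is Mild in mmol/L and Moderate in mg/dL. That is true and the correction does not cure it, but it concerns one value at a boundary, whereas the wrong figure removes half the band.

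**Conclusion.** The concern holds: wrong as written, and minor. The conversion result rests on no assumption beyond the unit factor, and the three factors tried agree to 0.004 mmol/L. The practical size depends on site units and episode counts, which the documents do not give; SAP 5.3.1 lists eight countries and no units. The range is:

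- All sites in mg/dL: no effect.
- Mixed units: the same glucose is graded at some sites and ungraded at others.
- All sites in mmol/L: consistent grading, but with a Mild band that ends at 59.5 instead of 65 mg/dL.

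The effect is confined to the grading of measured, self-treated mild episodes. The primary, key secondary and planned safety analyses are untouched.

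**What to change.** In the Mild bullet of Protocol 9.5.4.2, change the upper limit from 3.3 to 3.6 mmol/L. If the CRF Completion Guidelines or eCRF edit checks repeat the figure, change it there too.

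The cost is one figure, with no change to the SAP. Episodes already recorded could be regraded by program, but only if the eCRF holds the numeric glucose together with self-treatment, help, intravenous glucose and symptoms, since glucose alone does not assign the category. No planned analysis needs that regrade.
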